Cover Page

Official Title: Evaluating the Effectiveness of Migraine CarePath

NCT Number: NCT05067725

Date of document creation: 10/10/2022

Statistical Analysis Plan

The CMSL sites will be clustered-randomized based on clinic location, patient volume and patient to provider ratio to the intervention and control arm. Baseline characteristics (e.g. sex, age, race, ethnicity, insurance plans etc.) will be collected and compared between groups to ensure consistency for the investigation of all aims and sub-aims. Where applicable, statistical tests will be 2-tailed. T-tests will be used to measure the statistical significance of continuous data between groups. Chi-Square tests will be used to measure the statistical significance of categorical data.

All primary and secondary outcomes will be assessed using a GLM model and appropriate link and distribution, e.g. multivariate Poisson/Linear regression with robust standard errors. We will check model assumptions and power to produce constructive analysis and determine the effects of the interventions on the final outcomes. All analyses will be two-tailed and results will be reported both as effect estimates (with standard errors and p values) as well as effect estimates with 95% confidence intervals. We will estimate average treatment effects (ATEs) to mitigate biases in intervention-control group comparisons. These biases arise from permanent differences between the groups as well as biases in pre-post comparisons resulting from secular trends unrelated to the intervention. In the simplest case, program effects are assessed by comparing pre-post differences in outcomes between practices exposed (Y12–Y11) and not exposed (Y22– Y21) to the BPA, i.e. (Y12-Y11)-(Y22-Y21). We will calculate program effects on practicelevel outcomes using a semi-parametric, causal analysis if required. We will compare differences in outcomes between intervention and control practices. Multiple periods will be examined, when possible, to assess potential "burn-in" (effects of the intervention). Demographic variables that are significantly different between groups (p < 0.05) will be included in a multivariable (adjusted) model.

The analysis will be conducted based on the principle of "intention-to-treat (ITT)." All patients who consented and met the inclusion criteria will be included in the analysis per the group they were recruited into. For missing data via survey collection inclusion of only patients who completed all 3 sets of questionnaires could bias results toward improvement. To minimize this potential bias, a last observation carried forward (LOCF) technique will be applied. Results from the LOCF technique will be further compared to those from the measured data to assess the impact of loss to follow u

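### The outcome models do not carry the cluster design: standard errors are not tied to clinic, and the covariate rule would not bring in the factors used to allocate clinics

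*SAP*

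**What the plan says.** The first paragraph of the SAP sets the design: "The CMSL sites will be clustered-randomized based on clinic location, patient volume and patient to provider ratio to the intervention and control arm". The three factors are attributes of clinics, and the document does not mention them again.

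The second paragraph gives the model: "All primary and secondary outcomes will be assessed using a GLM model and appropriate link and distribution, e.g. multivariate Poisson/Linear regression with robust standard errors". It lists no covariates and does not say at what level the errors are robust. The paragraph ends with the only covariate rule: "Demographic variables that are significantly different between groups (p < 0.05) will be included in a multivariable (adjusted) model".

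The same paragraph writes out one contrast, (Y12 − Y11) − (Y22 − Y21), introduced by "In the simplest case, program effects are assessed by comparing pre-post differences in outcomes between practices exposed". Shortly afterwards it adds: "We will compare differences in outcomes between intervention and control practices". That sentence can mean the pre-post contrast again or a comparison of outcome levels. The SAP does not say which contrast is the main analysis.

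**The concern.** When clinics are allocated so as to balance factors that predict the outcome, the treatment contrast truly varies less. An analysis gains from this only if it includes those factors. The SAP's rule would not bring them in, because they are not demographic variables. Even if the rule covered them, balanced allocation makes them unlikely to differ at p < 0.05. So the models would pick up whatever happened to be imbalanced and leave out what the design balanced.

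The level of the standard errors is open as well. Clinics are randomised, so errors that treat patients as independent understate the uncertainty of a level comparison.

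What is at stake depends on how the gaps are filled: a loss of precision if errors are at clinic level, or too many false positives if they are at patient level.

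**Working it through.** **Inputs.** The SAP supplies two-sided tests and 95% intervals. It gives no number of clinics, cluster size, ICC, effect size or power, so there is no stated figure to reproduce. Everything below is assumed: k clinics split equally between arms, 30 patients per clinic, total variance 1, ICC 0.05, effect 0.3 SD, and allocation in two strata. R is the share of between-clinic variance that the stratum carries.

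**Level comparison, clinic-level errors.**
- Variance of a clinic mean, ignoring the stratum: 0.05 + 0.95/30 = 0.0817. At k = 12, the SE of the arm difference is √(4/12 × 0.0817) = 0.165.
- With the stratum balanced by design, the true variance is 0.05(1 − R) + 0.0317. For R = 30 / 50 / 70% this is 0.0667 / 0.0567 / 0.0467, giving SEs of 0.149 / 0.137 / 0.125.
- A model without the term therefore reports an SE roughly 11 / 20 / 32% too large (0.165 divided by each).

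Power with the term, from the noncentral t with 9 degrees of freedom and noncentrality 0.3/SE = 2.01 / 2.18 / 2.41, is 44 / 50 / 57%. Simulation (8,000 runs per cell, k = 12) agrees:

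| R | Type I error without term | Power without term | Power with term |
|---|---|---|---|
| 30% | 3.0% | 34% | 43% |
| 50% | 1.8% | 32% | 49% |
| 70% | 0.9% | 30% | 58% |

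A separate simulation of the level comparison (20,000 runs per cell) found the mean bias of the unadjusted estimate to be under 0.004 SD in every cell. In its two-stratum setting, which gives a smaller gain, power was 37 / 36 / 35% without the term and 41 / 44 / 47% with it at 12 clinics.

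**The same comparison when the factors do not matter (R = 0).** Power without and with one stratum term is 17 and 15% at 6 clinics, 24 and 23% at 8, about 37 and 37% at 12, and 60 and 60% at 20. Entering all three factors separately costs more. With the effect set at 2.8 standard errors and 8 clinics, power falls from 63 to 54% at R = 0 and from 66 to 62% at R = 30%.

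**Level comparison, patient-level errors.**
- R = 0: the design effect is 1 + 29 × 0.05 = 2.45, and √2.45 = 1.565. The nominal 5% test rejects when |z| exceeds 1.96/1.565 = 1.252, so type I error is about 21%.
- R = 70%, term omitted: the variance ratio is 30 × 0.0467 = 1.40, and 1.96/√1.40 = 1.656, so type I error is about 10%.
- R = 70%, term included: 1.40/(1 − 0.7 × 0.05) = 1.451, and 1.96/√1.451 = 1.627, so type I error is again about 10%.

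Simulation gave 10 to 22%, with or without the term.

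**Pre-post contrast.** The missing-data paragraph refers to "patients who completed all 3 sets of questionnaires", so the survey outcomes are repeated in the same patients. With an assumed within-patient correlation of 0.5 and clinic effects constant over time, those effects cancel. The variance of a clinic's mean change is 2 × (1 − 0.5) × 0.95/30 = 0.0317. At 12 clinics the SE is √(4/12 × 0.0317) = 0.103, and power is 75% without the term and 74% with it. At 6 clinics the SE is 0.145, and power is 35 and 30%. Only if clinics differ in their change does the term help: with a clinic variance of change of 0.05, of which the factors explain 30 / 50 / 70%, power at 12 clinics is 37 / 36 / 36% without and 41 / 44 / 48% with.

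**The case against.** The strongest reply is that the only contrast the SAP writes as a formula is pre-post, and it explains why: "These biases arise from permanent differences between the groups". For that contrast, omitting the factors costs almost nothing and including them can lose power when clinics are few. This stands, and it is why the precision point is limited to models that compare outcome levels. It does not dispose of the point, because the SAP calls the formula the simplest case, applies a GLM to every outcome, and does not name a main analysis.

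Second, the gain from adjustment has no fixed sign. With few clinics and weak prognostic strength it is nil or negative. This stands too, and it rules out fixed cut-offs by number of clinics, since any such cut-off would rest on assumed inputs.

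Third, the SAP does not forbid the allocation factors. Its model is given as an example, and its covariate rule does not claim to be exhaustive. That is correct: they are unspecified, not excluded, and the details of the allocation may be in the protocol. But the SAP does state a selection rule, and that rule follows observed imbalance.

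A reader might also infer that leaving out the factors biases the effect or raises the false-positive rate. Neither is so. With clinic-level errors the test becomes conservative, and the false-positive risk comes only from errors not tied to clinic. Nor does the SAP say that its errors are at patient level; it leaves the level open.

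**Conclusion.** The point holds as a minor one. In a model comparing outcome levels, the covariates would be chosen by observed imbalance and the level of the standard errors is unstated. If the errors are at clinic level and the allocation factors are prognostic, precision is lost without bias. Under the assumed inputs with 12 clinics and a stratum carrying 30 to 70% of clinic variance, the loss is about 9 to 28 points of power (43 − 34 and 58 − 30). If the errors are at patient level, type I error is about 10 to 22% in the same setting, and adding the factors does not cure it. For the pre-post contrast with time-constant clinic effects, omission costs close to nothing.

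These sizes illustrate the mechanism. They are not estimates for this trial, since the document gives no number of clinics, ICC, cluster size, effect or prognostic strength. It does not support a claim that the trial as planned loses any particular amount of power.

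**What to change.** Replace the open wording with three statements:

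1. All between-arm outcome analyses use standard errors at clinic level, with a small-sample correction.
2. Models comparing outcome levels include, irrespective of observed balance, the stratum or summary measure actually used to allocate clinics. It is entered as a prespecified term, with as few clinic-level terms as the number of clinics allows.
3. The SAP states whether (Y12 − Y11) − (Y22 − Y21) is the main analysis. If it is, the allocation term is optional there, and worthwhile only if the factors are expected to predict change.

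If allocation used no single stratum or summary, the SAP should say how the three factors will be reduced to one.

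The change is to wording only; the factors describe the clinics and were needed to allocate them. The downside is a few points of power if clinics are few and the factors are not prognostic: in the assumed level comparison, about 2 points for one term at 6 clinics and about 1 at 8. Clinic-level errors will also give wider intervals than patient-level ones wherever outcomes cluster by clinic, which is the uncertainty that the design implies.

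### Clinic sites are randomised, but the outcome GLM's robust standard errors are not tied to the clinic, so a patient-level analysis that ignores within-clinic correlation would comply with the SAP

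*SAP*

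**What the plan says.** The SAP's first paragraph sets the unit of randomisation: "The CMSL sites will be clustered-randomized based on clinic location, patient volume and patient to provider ratio to the intervention and control arm". Its second paragraph gives the analysis of all primary and secondary outcomes: they are "assessed using a GLM model and appropriate link and distribution, e.g. multivariate Poisson/Linear regression with robust standard errors". The same paragraph promises that "results will be reported both as effect estimates (with standard errors and p values) as well as effect estimates with 95% confidence intervals".

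Two further analyses follow there. In the simplest case, "program effects are assessed by comparing pre-post differences in outcomes between practices exposed" to the alert with those not exposed, which is a difference-in-differences. Then: "We will calculate program effects on practicelevel outcomes using a semi-parametric, causal analysis if required". Several periods may be examined where possible.

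The intention-to-treat paragraph defines the analysis set by patient: "All patients who consented and met the inclusion criteria will be included in the analysis per the group they were recruited into".

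Clustering is mentioned only for the randomisation. The text names no clustering level for the standard errors, no clinic effect, no estimating-equation method and no degrees of freedom based on the number of clinics. It gives no variance for the difference-in-differences or the practice-level analysis.

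**The concern.** Patients at one clinic share providers, case mix and the allocated arm, so their outcomes are likely to be correlated. The precision of the arm comparison then depends on the number of clinics as well as the number of patients. Robust standard errors can mean errors robust to unequal variances, which treat patients as independent, or errors clustered on a named unit, which do not. The SAP does not choose, and it offers the phrase only as an example.

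Standard errors, p-values and confidence intervals all depend on that choice. Two analysts who both follow the text could report different p-values for the same primary result. The variance method belongs in an analysis plan, so the absence of the protocol does not explain the gap.

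**Working it through.** **What the SAP supplies.** The unit of randomisation (clinic), the model (GLM, robust errors), two-tailed tests and 95% intervals. It gives no sample size, ICC, clinic size or number of clinics, so there is no figure to reproduce. Every input below is assumed. Total variance is 1 and the nominal level is 5%.

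**1. Post-period comparison, patients treated as independent.** With m patients per clinic, the design effect is DE = 1 + (m − 1) × ICC, and true type I error = 2 × [1 − Φ(1.96/√DE)]. For m = 20 and ICC 0.05, DE = 1 + 19 × 0.05 = 1.95, 1.96/√1.95 = 1.404, and the error is 16.0%.

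| ICC | m = 10 | m = 20 | m = 30 |
|---|---|---|---|
| 0.01 | 6.0% | 7.2% | 8.4% |
| 0.05 | 10.4% | 16.0% | 21% |
| 0.10 | 15.5% | 25.0% | 32.1% |

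**2. Patient-level difference-in-differences, m = 30 per clinic and period.** Let r be the correlation of a clinic's effect between periods, and p the within-patient correlation (0 if new patients are measured, 0.5 if the same patients). The variance of one clinic's mean change is V = 2 × ICC × (1 − r) + 2 × (1 − ICC) × (1 − p)/m.

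- Four-cell test, all observations treated as independent. It assumes variance 2/m, so error = 2 × [1 − Φ(1.96 × √((2/m)/V))].
  - ICC 0.05, same patients, r = 1: V = 2 × 0.95 × 0.5/30 = 0.0317, 1.96 × √(0.0667/0.0317) = 2.84, error 0.4%.
  - ICC 0.05, new patients, r = 0.5: V = 0.05 + 0.0633 = 0.1133, 1.96 × √(0.0667/0.1133) = 1.50, error 13.3%.
- Patient change scores, p = 0.5. The assumed variance is [2 × ICC × (1 − r) + (1 − ICC)]/m.
  - ICC 0.05: the error is 5.0%, 12.1% and 21% at r = 1.0, 0.8 and 0.5.

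Over both tests and r from 1.0 to 0.5, the same formulas give 0.5% to 8.4% at ICC 0.01, 0.4% to 21% at 0.05, and 0.3% to 32.1% at 0.10. The test can therefore be conservative or liberal.

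**3. Errors clustered on clinic, no small-sample correction.** With G equal-sized clinics and k = G/2 per arm, the uncorrected variance is too small by (k − 1)/k on average. Comparing with 1.96 gives error = 2 × P(t with G − 2 df > 1.96 × √((k − 1)/k)).

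| Clinics | Effective cut-off | Type I error |
|---|---|---|
| 6 | 1.600 on 4 df | 18.5% |
| 10 | 1.753 on 8 df | 11.8% |
| 20 | 1.859 on 18 df | 7.9% |

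Multiplying the variance by G/(G − 2) and using t with G − 2 df restores 5.0% when clinics are equal in size. It does not when they are unequal. In simulation with clinics of 10 to 50 patients, ICC 0.05, r = 0.8 and the same patients in both periods, that version gives 8.3%, 6.6% and 5.7% at 6, 10 and 20 clinics. Patient volume enters the allocation, so sizes may well differ, and the correction has to be named. CR2 with Satterthwaite degrees of freedom stays close to 5% in that unequal setting.

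**The case against.** The strongest reply is that, in a plan that opens by cluster-randomising sites, robust is naturally read as cluster-robust. That is fair: the wording is ambiguous, not wrong. A reader might infer that the SAP has chosen to ignore clustering. It nowhere says so, and the figures in steps 1 and 2 describe readings that it permits, not an error that it commits. The reply still leaves a gap, because clinic-clustered errors without a small-sample method reject too often when clinics are few.

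A reader might also infer that the practice-level difference-in-differences has the same defect. The text does not support that. It speaks of exposed and unexposed practices and of practice-level outcomes; with one value per practice and period, the randomised unit is already the unit of analysis. What is missing there is a small-sample method and, if several periods are used, a way to handle correlation over time. The semi-parametric step is only conditional ("using a semi-parametric, causal analysis if required"), so it cannot settle the variance of the GLM that covers every outcome.

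A third objection is that the size is unknown. This stands in full. At ICC 0.01 the inflation in step 1 is modest, and for a patient-level difference-in-differences even the direction depends on how far clinic effects drift and whether patient pairing is modelled.

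**Conclusion.** The point holds in this form: the SAP randomises clinics but does not tie the variance of its outcome GLM to the clinic, so it permits a patient-level GLM or difference-in-differences whose p-values and intervals may be invalid. This is certain from the text and does not depend on any assumed number.

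The size is illustrative only. On assumed clinics of 10 to 30 patients and ICC 0.01 to 0.10, an unadjusted post-period patient-level test has a true error of about 6% to 32%. Clustering without correction gives about 18.5%, 11.8% and 7.9% at 6, 10 and 20 equal-sized clinics. None of these is an estimate for this trial.

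A reader might go further and conclude that the GLM should give way to a clinic-level t-test as the primary analysis. The documents give no ground for that. An unweighted test on clinic means estimates the effect for the average clinic rather than the average patient, replaces a rate ratio with a difference in means for Poisson outcomes, and needs a two-stage step for the planned covariate adjustment. Nor can its degrees of freedom be fixed at the number of clinics minus 2 without knowing whether the allocation was stratified or matched, which the SAP leaves unclear.

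**What to change.** Keep the GLM. Replace the open reference to robust errors in the SAP's second paragraph with:

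> *with standard errors clustered on clinic (the unit of randomisation), using a bias-reduced (CR2) variance with Satterthwaite degrees of freedom, for all primary and secondary outcomes including the difference-in-differences and any multi-period analysis; any factor used to stratify or match clinics in the allocation is reflected in the model.*

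Add a t-test on clinic-level pre-post changes as a sensitivity analysis, with degrees of freedom that match the allocation. It is most useful if clinics are few.

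The cost is SAP wording and standard software. Intervals will usually be wider. With equal-sized clinics and no stratification or matching, the ratio to an uncorrected clinic-clustered interval is (t₀.₉₇₅ on G − 2 df)/1.96 × √(k/(k − 1)), which is 1.73, 1.32 and 1.13 at 6, 10 and 20 clinics.

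### Covariates enter the adjusted model on a baseline p-value: this selects on observed imbalance rather than prognosis, by tests that ignore clinic (minor, cheap to repair)

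*SAP*

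**What the plan says.** The last sentence of the SAP's second paragraph gives the only covariate rule in the document: "Demographic variables that are significantly different between groups (p < 0.05) will be included in a multivariable (adjusted) model". The first paragraph sets the candidates and the tests. The candidates are illustrative and open-ended: "Baseline characteristics (e.g. sex, age, race, ethnicity, insurance plans etc.) will be collected and compared between groups". The tests are "T-tests will be used to measure the statistical significance of continuous data between groups" and "Chi-Square tests will be used to measure the statistical significance of categorical data".

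The same paragraph makes the site the unit of allocation: "The CMSL sites will be clustered-randomized based on clinic location, patient volume and patient to provider ratio to the intervention and control arm". Robust standard errors are mentioned for the outcome GLM, not for the baseline tests.

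Two kinds of contrast are described. One is a difference-in-differences: "In the simplest case, program effects are assessed by comparing pre-post differences in outcomes between practices exposed". The other is a direct comparison: "We will compare differences in outcomes between intervention and control practices". The SAP does not say whether the adjusted model is primary or supportive. The intention-to-treat paragraph adds: "All patients who consented and met the inclusion criteria will be included in the analysis per the group they were recruited into".

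**The concern.** A baseline test asks whether the arms differ on a variable. It does not ask whether the variable predicts the outcome. A prognostic variable just above 0.05 is left out, and an irrelevant one just below is put in.

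The trigger is also miscalibrated. Patients in one clinic tend to resemble each other, so a patient-level test between arms made of whole clinics rejects too often for any variable that clusters by clinic. Which variables are fitted is then partly accidental.

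What is at stake is some precision, the predictability of the adjusted model and, if recruitment followed site allocation and the arms really differ, bias that a fixed adjustment would have removed.

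**Working it through.** The SAP states no number of clinics, clinic size, ICC, effect size or power, so there is no figure to reproduce. Only the 0.05 cut-off comes from the document; every other input is assumed.

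**Assumed scenario.** 6 clinics per arm, 30 patients per clinic (180 per arm); outcome ICC 0.05; covariate ICC 0.02 to 0.10; correlation r of covariate with the analysed outcome 0.1 to 0.3; simple randomisation of clinics; linear model with clinic-robust standard errors, t on 10 df; true effect 0.513 SD for the power runs.

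1. **False-flag rate.** Design effect DE = 1 + 29 × ICC; flag rate = 2 × [1 − Φ(1.96/√DE)].
   - ICC 0.02: DE 1.58, rate 12%.
   - ICC 0.05: DE 2.45, rate 21%.
   - ICC 0.10: DE 3.90, rate 32% (33% by simulation).

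   Stratified allocation could lower these rates.

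2. **Jump at the cut-off.** When the baseline p-value crosses 0.05, the estimate moves by r × 1.96/√2.45 of its SE: 0.13, 0.25 and 0.38 SE at r = 0.1, 0.2 and 0.3.

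3. **Type I error.** By simulation, 5.3% to 6.1% under the rule and 5.8% to 6.2% when always adjusting. The excess over 5% comes from robust standard errors with 12 clinics, not from the rule.

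4. **Power.** At the nominal 5% level the rule trails always adjusting by 0.3 to 3.0 points. That comparison is not like for like, because always adjusting has the higher type I error. At r = 0.3 and covariate ICC 0.10, one set of runs gave 82.8% against 85.6%, with type I error of 5.4% against 6.2%. With size equalised, that gap falls to about 0.8 points. Across r of 0.1 to 0.3 the equal-size loss is about 0 to 1.7 points, and the SD of the estimate is 0.1% to 1.9% larger under the rule.

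5. **A real 0.2 SD arm difference (r = 0.3, covariate ICC 0.05).**
   - The naive SE of the covariate difference is √(2/180) = 0.105, so the flag threshold is 1.96 × 0.1054 = 0.207 SD.
   - The actual SE is √(2 × 2.45/180) = 0.165.
   - P(not flagged) = Φ((0.2066 − 0.2)/0.165) − Φ((−0.2066 − 0.2)/0.165) = Φ(0.04) − Φ(−2.46) = 0.51. So 49% are flagged.
   - Mean imbalance in unflagged trials = 0.2 + 0.165 × [φ(2.46) − φ(0.04)]/0.51 ≈ 0.077 SD. The bias is 0.3 × 0.077/0.165 ≈ 0.14 SE (simulation: about 0.13).
   - Averaged over all trials: 0.51 × 0.14 ≈ 0.07 SE (simulation: 0.06 to 0.08). Never adjusting gives 0.3 × 0.2/0.165 ≈ 0.36 SE (simulation: 0.37). Always adjusting gives 0.

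6. **Same-patient difference-in-differences.** A fixed demographic cancels from each patient's change, so adding it as a main effect does nothing. In one simulated data set of 360 patients the linear estimate was 0.5376 with or without it, and the Poisson estimate −0.2932 with or without it. A covariate-by-period term did move the linear estimate, to 0.4991.

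**The case against.** The best defence is that the rule does little harm and some good. It is mechanical, stated in advance and uses only baseline data and arm, so it gives no route to choosing covariates by their effect on the result. That stands, though the open-ended candidate list weakens it. If patients were recruited after sites were allocated, adjusting for observed imbalance is reasonable, and in step 5 the rule takes mean bias from 0.37 SE to about 0.07. That also stands: the fault lies in adjusting only when p < 0.05, not in adjusting.

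The only contrast the SAP writes out is the difference-in-differences, where a main effect makes no difference if the same patients are seen in both periods. This is right, but the SAP presents it as the simplest case and also plans a direct comparison of practices. The rule can matter there, where patients differ between periods, or where the variable relates to change.

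The protocol is not at hand and the SAP text breaks off in its last paragraph, so a further covariate rule may exist elsewhere. That limits the claim to this document. It does not rescue the rule that is stated.

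A reader might infer three stronger things. One is that testing baseline variables inflates the false-positive rate for treatment; step 3 shows it does not, and a high flag rate does not by itself bias the estimate. The second is that the rule costs up to 3 points of power; step 4 shows that part of that gap is the higher type I error of the comparator. The third is that the primary result is compromised; the SAP never calls the adjusted model primary.

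**Conclusion.** The point holds as a minor one. The stated rule chooses covariates by the wrong criterion, using tests that do not match the unit of randomisation. The measurable harm is a small loss of precision, an adjusted model that cannot be predicted before the data are seen, and residual bias when a real arm difference escapes the screen. These sizes rest wholly on the assumed clinic numbers, ICCs and correlations. The precision loss shrinks towards nothing if demographics are weakly prognostic, and if the adjusted model is only supportive the harm is confined to that result.

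**What to change.** Delete the p < 0.05 rule. In its place, name a short closed list of patient-level covariates that are already collected (for example age, sex and insurance), fitted whatever the observed imbalance. State how each enters the difference-in-differences model, for instance with a covariate-by-period term, since a main effect alone can leave the estimate unchanged. State whether the adjusted model is primary or supportive. The baseline comparison can remain as description, with nothing in the model depending on it.

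The cost is a change of wording and a few degrees of freedom. In the assumed scenario, unprognostic covariates raise the SE by 0.3% to 0.4% for two and 0.4% to 1.3% for five. Five at covariate ICC 0.10 also move robust-SE type I error from 5.7% to 6.5% with 12 clinics, so the list should stay short.

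The site-level allocation factors should not be forced in. With 6 clinics per arm and 80% power to start, three such terms would leave 76% if balanced across arms and about 62% if unbalanced and unprognostic.

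### For survey outcomes, LOCF cannot fill a missing first questionnaire, so it does not secure the stated inclusion of all consented, eligible patients

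*SAP*

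**What the plan says.** The SAP is unnumbered. Its final paragraph, on intention-to-treat and missing data, sets the analysis population: "All patients who consented and met the inclusion criteria will be included in the analysis per the group they were recruited into". Having returned a first questionnaire is not a condition.

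The same paragraph then turns to missing survey data. It warns that "inclusion of only patients who completed all 3 sets of questionnaires could bias results toward improvement" and answers: "To minimize this potential bias, a last observation carried forward (LOCF) technique will be applied". One check follows: "Results from the LOCF technique will be further compared to those from the measured data to assess the impact of loss to follow". The text breaks off there, so further rules may exist that cannot be seen.

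The preceding paragraph, on outcome models, describes the contrast. In what it calls the simplest case, "program effects are assessed by comparing pre-post differences in outcomes between practices exposed" and practices not exposed, written as (Y12-Y11)-(Y22-Y21). The general method is a GLM with robust standard errors. The SAP does not say whether a survey outcome enters as a patient's own change, as a follow-up value, or as a practice mean per period.

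**The concern.** The paragraph promises to analyse everyone who consented and was eligible. Its one visible device for doing so works in one direction only. LOCF copies an earlier answer to a later time; it has no means of producing the first answer. Any pre-post contrast needs a pre value. For a patient without set 1 the plan supplies neither that value nor a rule for doing without it.

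At stake is the kind of selection that the paragraph sets out to prevent. The survey analysis could carry an intention-to-treat label while resting, in whole or in its pre term, on patients who returned the first questionnaire. If that return differs between arms and is related to outcome, the estimated effect is biased.

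The planned comparison with measured data would not reliably reveal this. It is aimed at loss to follow-up. On a patient-level change, the LOCF analysis and the measured-data analysis both leave out patients without set 1, so the two could agree and reassure wrongly.

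**Working it through.** The SAP states no sample size, return rate or power figure, so there is none to reproduce. The check has three steps. The first is exact; the other two use assumed rates.

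**1. What LOCF can fill.** Each of the three sets is returned (1) or missing (0), giving 2 × 2 × 2 = 8 patterns. After LOCF:

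| Pattern (sets 1, 2, 3) | First value | Final value | Patient-level change |
|---|---|---|---|
| 1 1 1 | yes | yes | yes |
| 1 1 0 | yes | yes (from set 2) | yes |
| 1 0 1 | yes | yes | yes |
| 1 0 0 | yes | yes (from set 1) | yes (forced to 0) |
| 0 1 1 | no | yes | no |
| 0 1 0 | no | yes (from set 2) | no |
| 0 0 1 | no | yes | no |
| 0 0 0 | no | no | no |

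LOCF fills the first set in 0 of the 4 patterns where it is missing. A patient-level change exists in 4 of 8 patterns, exactly those with set 1. A final value exists in 7 of 8.

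**2. Patients and precision lost.** Let f be the share without set 1 (assumed).

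- A patient-level change keeps 1 - f of the promised population.
- A contrast of practice-period means keeps 1 - f in the pre mean. In the post mean it keeps between 1 - f (none of them answers later) and all (every one does).
- If non-return is unrelated to change, the SE of a patient-level change contrast is multiplied by 1/√(1 - f). At f = 0.05, 0.10 and 0.20 this is 1/√0.95 = 1.026, 1/√0.90 = 1.054 and 1/√0.80 = 1.118: increases of about 3%, 5% and 12%. The formula treats patients as independent. With clinics randomised, the between-clinic part of the variance does not shrink with patient numbers, so the increase would tend to be smaller.

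**3. Bias under each reading.** Large-sample simulation. Assumptions: SD 1; correlation 0.6 between adjacent sets and 0.5 between sets 1 and 3; lower scores better; true effect -0.20; sets 2 and 3 always returned; set 1 missing more often when the set 3 score is worse (log-odds slope 0.7 per SD). The contrast is set 3 minus set 1, intervention minus control.

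With set 1 missing in 7% of control and 21% of intervention patients:

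- Patient-level change, patients without set 1 dropped: -0.246. Excess (0.246 - 0.20)/0.20 = 23%, an overstatement.
- Period means using all available answers: -0.156. Shortfall (0.20 - 0.156)/0.20 = 22%, an understatement.
- All returned sets used, under missingness at random: -0.202.

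Over slopes of 0.5 to 1.0 the first runs from about -0.23 to -0.26 and the second from about -0.17 to -0.14. With 10% against 15% missing, the first is about -0.21 to -0.22. With 14% in both arms, still related to outcome, it is about -0.20, so there is essentially no bias.

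The opposite signs have a simple cause. Suppose that leaving out patients without set 1 shifts an arm's mean set 3 score by -d. With correlation ρ between sets 1 and 3 it shifts the mean set 1 score by about -ρd. Dropping these patients from both terms moves the change by -(1 - ρ)d. Dropping them from the pre term alone moves it by +ρd. At ρ = 0.5 the two are equal and opposite, and if d is the same in both arms both cancel.

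**The case against.** A reader might infer that patients without set 1 have nothing to carry forward, that they drop out of the pre-post contrast, and that the population statement and LOCF therefore cannot both hold. The document does not support this.

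- Strictly, nothing can be carried only for a patient who returned no questionnaire. With set 2 in hand, LOCF can still fill set 3.
- Leaving the contrast follows only for a patient-level change. The SAP words the contrast as between practices, and only as the simplest case. With period means, a patient with a later questionnaire still contributes to Y12 or Y22. Nor does the SAP say that set 1 supplies Y11 or Y21 for survey outcomes, or that later answers are discarded.
- LOCF is the only missing-survey rule in the surviving text, which breaks off mid-word.
- The protocol is not shown. If it obtains set 1 at consent, or requires it for eligibility, few or no patients are affected. The paragraph's attention to loss to follow-up suggests that its authors had later dropout in mind.
- A bias of a quarter is not established either. It comes from a scenario with three times the non-return in one arm, and its direction depends on which reading is used. The likelihood method does well there partly because missingness was made to depend on a score that the model observes.

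All of this stands, and it narrows the point to survey outcomes with a missing first set. It does not remove it. Under the practice-level reading, the pre and post means rest on different patients, which is no safer. It could also be said that one clarifying sentence would do and that changing the model is a matter of taste. A sentence would settle who enters and how, but if set 1 can be missing, no wording makes LOCF supply it; a model of all returned sets does without it.

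**Conclusion.** The concern holds in a limited form. For survey outcomes, the one missing-data rule visible in the SAP cannot fill a missing first questionnaire, so it does not secure the population that the SAP promises. That step is logic and needs no assumed rate.

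The consequence is conditional. If non-return of set 1 differs by arm and relates to outcome, the estimate is biased: away from zero for a patient-level change and towards zero for period means in the scenario examined, by roughly a fifth to a quarter at 7% against 21% missing. If non-return is equal by arm and relates to outcome in the same way in both, bias is about nil, and a patient-level change loses mainly precision (SE up about 3% to 12% at 5% to 20% missing). All these rates are assumptions. If set 1 is always obtained at consent, the point is moot.

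This should be corrected before analysis. Confidence is medium, because the protocol and the end of the paragraph are not available.

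**What to change.** For survey outcomes, make the main analysis a likelihood-based repeated-measures model. Suggested text:

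> *Every questionnaire returned by a consented, eligible patient enters one likelihood-based repeated-measures model, with all three sets as responses, arm-by-set terms and allowance for clustering by clinic. A missing first set does not remove a patient. LOCF is used, if at all, as a sensitivity analysis. Patients who returned no questionnaire cannot contribute; they are counted by arm. The survey analysis set is described as consented, eligible patients with at least one questionnaire.*

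The arm-by-set terms give the difference-in-differences directly, so the SAP's contrast is kept, and the choice between patient-level change and period means no longer determines who is counted. If set 1 is always collected at consent, one sentence saying so closes the point about the first set.

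The cost is SAP wording and a standard mixed-model analysis, with no new data. There are two small downsides. The model assumes that missingness is at random given the returned answers, and the survey set gives up the plain intention-to-treat label.
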